11.3.2 Source document verification

Unless agreed in writing, all data collected in the eCRF must be verifiable by the source data. Therefore it is the Investigator's responsibility to ensure that all relevant data is clearly recorded in the medical records. The Investigator must allow the RM-CTU direct access to relevant source documentation for verification of data entered into the eCRF, taking into account data protection regulations. Entries in the eCRF will be compared with patients' medical records and trial source data using a risk-based approach and the verification will be documented in the monitoring report.

The patients' medical records, and other relevant data, may also be reviewed by appropriate qualified personnel independent from the Sponsor appointed to audit the trial, and by REC and regulatory authorities. The Sponsor and its representatives may look at and analyse patients confidential medical information in any country worldwide. Details will remain confidential and patients' names will not be recorded outside the hospital.

11.3.3 Clinical study report

At appropriate intervals, including for the purpose of dose escalation decisions, interim data listings will be prepared to give the Investigator and analysing laboratories the possibility to review the data and check the completeness of information collected. The dose escalation stage of the trial is expected to take approximately 18 months to establish the MTD. It is anticipated that a trial report will be generated after approximately 24 months to describe initial safety data and any early efficacy signal. The dose expansion stage is expected to take 24 months to complete. During this stage, reports will be generated on a quarterly basis. These will outline patient demographics, and describe emerging toxicity and efficacy data.

All clinical data will be presented at the end of the study on final data listings. The CI, along with the Sponsor-appointed statistician will prepare a clinical study report based on the final data listings. The report will be submitted to the Investigator(s) for review. A summary of the final clinical report must be provided to the MHRA and to the Research Ethics Committee. These results may also be made available to commercial third parties.

11.3.4 Record retention

During the clinical trial and after trial closure the Investigator must maintain adequate and accurate records to enable both the conduct of a clinical trial and the quality of the data produced to be evaluated and verified. These essential documents (as detailed in Chapter V of Volume 10 (Clinical Trials) of The Rules Governing Medicinal Products in the European Union based upon Section 8 of the ICH GCP Guidelines), including source documents such as scans, trial related documents and copies of the eCRFs, associated audit trail and SAE report forms, shall show whether the Investigator has complied with the principles and guidelines of Good Clinical Practice (GCP).

All essential documents required to be held by the Investigator must be stored in such a way that ensures that they are readily available, upon request, to the Regulatory Agency or Sponsor, for the minimum period required by national legislation. Records must not be destroyed without prior written approval from the Sponsor.

The medical files of trial patients shall be retained in accordance with national legislation and in accordance with the maximum period of time permitted by the hospital, institution or private practice.

11.3.5 Ethical considerations

The Trial will be conducted in accordance with the ethical principles founded in the Declaration of Helsinki (2013, Appendix 1). Before starting the trial, the protocol, patient information sheet and consent form must be approved by a Research Ethics Committee and to the relevant regulatory authorities.

It is the Chief/Principal Investigator's responsibility to update patients (or their authorised representatives, if applicable) whenever new information (in nature or severity) becomes available that might affect the patient's willingness to continue in the trial. The

Chief/Principal Investigator must ensure this is documented in the patient's medical notes and the patient is re-consented, where appropriate.

11.3.6 Risk mitigation

Although panRAF inhibition is not an established therapeutic strategy, the targeting and inhibition of intracellular kinases and in particular BRAF targeting has been extensively studied both experimentally and clinically. RAF kinases therefore represent a validated therapeutic target (particular in melanoma where disease pathogenesis is highly dependent on the aberrant function of the MAPK pathway via these kinases) that warrants further clinical investigation.

This trial does not represent a 'first in class' project, as the extensive experimental and clinical experience of kinase inhibitors (such as sorafenib) and BRAF inhibitors (such as vemurafenib) can be drawn upon to predict potential risks due to panRAF inhibition and to allow planning to mitigate these anticipated risks associated with panRAF inhibition.

As a 'first in man' trial, patient safety is of paramount concern during this trial. Whilst all aspects of the trial have been designed with patient safety in mind, the following design aspects have been incorporated to ensure that (particularly during all dose escalation stages) an individual patient's risk is minimised:

- Each patient will have a single dose 'run-in' 3-7 days prior to commencement of continuous dosing
- Patients will be admitted for observation and PK assessments for 48 hours after 1st dose administration of the continuous dosing i.e. Cycle 1 Day 1
- One patient will commence a dose cohort, with at least 7 days delay between the first and any subsequent patients being dosed within that cohort
- All emerging toxicities will be reviewed and graded in real time
- Decisions to dose escalate will be made by a panel of clinicians, including an independent chair and other independent physicians, to ensure independence and safety

The toxic effects (and associated risks) relating to the panRAF inhibitor therapy are not yet established. Unknown risks will be mitigated against with the usual comprehensive approach to clinical observation and routine investigation/assessment that is required in any clinical trial. panRAF inhibitor therapy may induce toxic effects similar to those seen with RAF or other kinase inhibitors. These potential risks will be mitigated against with the specific steps as outlined in Table 16.

Table 16: Mitigation of potential risks

Potential Risk	Mitigating Steps in Trial
Skin reactions /malignancies	Regular scheduled clinical review and examination (including palms and soles) with referral for dermatology review/treatment of lesions.
Arthralgia	Regular scheduled clinical review and examination.

Myositis	Regular scheduled clinical review and examination; monitoring of blood tests (e.g., CK); referral for further specialist review as necessary.
Alopecia	Regular scheduled clinical review and examination.
Fatigue	Regular scheduled clinical review and examination.
Uveitis/Iritis	Regular scheduled clinical review and examination with referral to Ophthalmology for review of any concerning symptoms.
Vasospasm	Regular scheduled clinical review and examination with referral for further specialist review as necessary.
Slow wound healing	Patients requiring major surgery to be excluded from trial.
Febrile reactions	Clinical observations including temperature measurement.
Haematological abnormalities such as anaemia or thrombocytopenia	Routine haematology blood test monitoring.
Biochemical abnormalities such as altered liver function tests	Routine biochemistry blood test monitoring.
ECG changes eg QTc prolongation	Exclusion of patients with baseline QTc prolongation (> 450 ms). Exclusion of patients with uncontrolled hypertension on > 1 antihypertensive. ECG monitoring of patients during treatment and central analysis of ECGs for any effects on QTc interval, and exclusion of patients if QTc interval becomes > 500 ms.
Left ventricular dysfunction (eg reduced LVEF)	Baseline echocardiography to exclude patients with inadequate LVEF (< 50%). Repeat monitoring with echo at 1 month and thereafter if symptoms of dysfunction develop.
Embryo-fœtal toxicity	Measures to avoid pregnancy as described in section 9.6.
Any signal emerging during clinical study	Ongoing monitoring by the SRC.

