1.2 Study rationale

1.2.1 Rationale for study design

This is an open-label, multi-centre dose escalation (Part A) and dose expansion (Part B) study of CCT3833, administered orally to patients with advanced solid malignancies, including melanoma. The study design allows an escalation of dose with intensive safety monitoring to ensure the safety of patients. In Part A patients will be recruited as part of a rolling six design.

This study is designed such that in Part A, for the first cycle for each cohort, patients are given a single dose of CCT3833, followed by at least a 48-hour washout period, then continual once-daily dosing. Inclusion of this single dose and interval prior to multiple dose administration will permit assessment of single dose safety and will allow characterisation of both single and continuous dose PK and PD effects of CCT3833. For the first cohort, the starting dose will be 20 mg per day.

Part B will dose additional melanoma patients in 28-day cycles at the maximum tolerated dose (MTD), or at lower doses shown to be biologically active, safe and tolerable in Part A, in order to further explore tolerability and PK/PD effects, and to provide preliminary efficacy information.

There is currently no clinical experience with CCT3833. However, based on the preclinical safety and toxicology studies, a careful safety evaluation package has been

put in place to minimise the potential risk to patients and to discover potential toxicities in a timely manner.

Careful consideration has been given to the MHRA guidelines regarding the mitigation of risk in first-in-human clinical trials (see section 11.3.6); with regard to the mode of action, the nature of the target, and relevance to animal models, CCT3833 is regarded as low risk. CCT3833 does not meet the risk criteria defined by the UK MHRA Expert Advisory Group (EAG).

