6.2 Selection of the Phase 1 starting dose

The starting dose of CCT3833 is 20 mg, taken as two 10 mg capsules. The starting schedule is a once daily continuous dosing schedule, but other dosing regimens may be considered depending on tolerability and exposures.

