6.4 Definition of dose-limiting toxicity

The dose-limiting toxicity (DLT) is defined using the National Cancer Institute's (NCI) Common Terminology Criteria for Adverse Events (CTCAE) version 4.03 (Appendix 4). DLTs identified in Cycle 1 of treatment will inform the decision to dose escalate through the increasing dose levels. Significant toxicities and DLTs in later cycles will be considered throughout the treatment period and in determining the recommended Phase 2 dose.

A DLT is defined as a probably or highly probably drug related toxicity as detailed in Table 8.

Table 8: Dose-limiting toxicity definitions and criteria

Toxicity	Criteria
Any toxicity causing a decrease in treatment dose intensity	Inability to deliver > 75% of the planned dose intensity in a cycle due to CCT3833-related toxicity
Haematology	
 • Grade 4 neutropenia for > 1 week • Grade 4 thrombocytopenia or grade 3 thrombocytopenia with bleeding • Febrile neutropenia • Grade 4 anaemia (unless a specific cause of blood loss is identified)
Cardiovascular	
 • Any grade 3 or above • Hypertension (grade 3 or above) lasting more than 2 weeks despite optimal treatment
Skin	Any grade 3 or above, persisting for > 7 days despite optimal treatment
Metabolic	Grade 3 or above hyperglycaemia (measured in the fasted state)
Any other drug related G3/4 toxicity except:	
 • Alopecia • Nausea that is sub optimally managed • Vomiting that is sub optimally managed • Diarrhoea that is sub optimally managed • Constipation that is sub optimally managed
Any other toxicity that is considered dose-limiting in the view of the Investigator	

Baseline laboratory values are those reported before the first dose of CCT3833.

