6.6 Dose escalation scheme

Patients will be enrolled to ensure a minimum of 3 and a maximum of 6 evaluable patients per cohort. The dose level of CCT3833 will be assigned using all available data by the Sponsor in conjunction with the Safety Review Committee (SRC). Dose assignment will be made after considering the number of patients already enrolled at the current dose level, the number of DLTs (and any other drug related AEs) observed at the current dose level, and the number of patients enrolled who are at risk of developing a DLT.

The first patient in all cohorts will be treated for 7 days taken from Day 1, before the second and third patients can take their first dose of CCT3833 in parallel. Patients who receive less than 75 % of their planned doses in Cycle 1, taken from Day 1 onwards, for reasons other than toxicity will not be evaluable for assessment of DLT for dose review decisions and will be replaced in the cohort.

In order to make the decision to escalate the CCT3833 dose, three evaluable patients must have completed one cycle of treatment (28 days). The time between cohorts is therefore approximately 6 weeks.

The dose increases between cohorts will be up to 100%, i.e. doubling of the dose (dosed on a flat scale and not by body weight or body surface area), until a probable or highly probable drug-related CTCAE v4.03 (Appendix 4) Grade 3 AE (or grade 4 haematological toxicity) is reported. Subsequent dose increases between cohorts will be driven by reported safety data and available PK and PD data. The available PK data for all patients will be reviewed as part of the dose escalation data. PK data for a minimum of two patients in the current cohort will be required to inform dose review decisions. PK data for a minimum of two patients from the previous cohort will also be required.

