6.9 Dose modifications

6.9.1 Dose reductions

The dose of CCT3833 will be reduced to the previous dose level for any patient who experiences a DLT (which can occur during any cycle of treatment). Once the dose has been reduced, it should not be re-escalated. If any patient requires more than two dose reductions, the patient should be withdrawn from the study by the Principal Investigator.

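### Table 16's on-treatment QTc > 500 ms stop is not carried into the dose-modification, discontinuation or ECG sections; above 20 mg, 6.9.1 directs a dose reduction if the event is scored as a DLT

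*Combined protocol and SAP*

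**What the plan says.** Section 11.3.6 introduces its table of risks with a commitment: "These potential risks will be mitigated against with the specific steps as outlined in Table 16". For QTc prolongation, Table 16 lists a baseline exclusion (above 450 ms), ECG monitoring on treatment, central analysis of the ECGs, and "exclusion of patients if QTc interval becomes > 500 ms". The last item is an on-treatment rule, because the baseline limit stands separately in the same cell. Section 1.2.1 cites 11.3.6 as the place where first-in-human risk is addressed.

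Section 6.9.1 sets the action after a dose-limiting toxicity in any cycle: "The dose of CCT3833 will be reduced to the previous dose level for any patient who experiences a DLT". Its only withdrawal rule is: "If any patient requires more than two dose reductions, the patient should be withdrawn from the study by the Principal Investigator". It has no QTc exception.

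On what counts as a DLT, 6.4 states: "A DLT is defined as a probably or highly probably drug related toxicity as detailed in Table 8". Table 8 includes cardiovascular toxicity of grade 3 or above, and any other toxicity that the Investigator judges dose-limiting.

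Section 6.12 lists reasons for which the Investigator may discontinue a participant. They include an adverse event that requires stopping the drug, and ineligibility that arises during the trial. QTc is not named.

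**The concern.** A stopping rule works only if the people dosing patients meet it where they look for instructions. Here the rule sits in an administrative section near the end of the protocol. The section that tells sites what to do after a serious toxicity gives a different instruction for the same event, if that event is scored as a DLT.

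The stake is continued exposure of a patient with marked QTc prolongation to a drug with no previous human experience. Section 1.2.5 says that, because of what is known about related products, individual cardiovascular findings in the non-clinical work deserve more weight than usual. The protocol evidently meant this risk to be controlled tightly.

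**Working it through.** The check is a comparison of text. The plan gives no figure to reproduce.

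1. **Where the 500 ms limit appears.** Once, in Table 16. It is absent from 6.3, 6.4, 6.9.1 to 6.9.3, 6.12, the ECG paragraphs of 8.1.2.2 and 8.2.2.1, and the footnotes to Tables 14 and 15. The only other QTc limit is 450 ms at baseline (4.3, repeated in 1.2.5). The ECG paragraphs ask for review of the Fridericia-corrected QTc but attach no threshold or action. Tables 12 and 13 could not be checked.

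2. **When 6.9.1 applies.** The event must be a DLT, which needs two things: causality rated probable or highly probable, and either cardiovascular grade 3 or above or an Investigator judgement that it is dose-limiting. That a QTc above 500 ms reaches grade 3 is an assumption, because Appendix 4 refers to the CTCAE without reproducing the grades.

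3. **Actions for the same event, scored as a DLT.**
   - Table 16: the patient is excluded.
   - 6.9.1: the dose goes down one level. Up to two reductions are possible, and withdrawal is required only when a third is needed.
   - 6.12: the Investigator may discontinue, but need not.
   - 6.9.2: no direct contradiction, since an excluded patient has no next cycle. Read alone, it would allow a restart after recovery within two weeks.

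4. **At the starting dose.** "The starting dose of CCT3833 is 20 mg, taken as two 10 mg capsules", and no lower level is given. The 6.9.1 instruction therefore has no defined target at 20 mg, and the conflict arises only above it.

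5. **If the event is not a DLT** (for example, causality only possible). Section 6.9.1 is silent, so nothing contradicts Table 16. The stop is still missing from section 6, where only the delay rule and Investigator discretion remain.

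6. **What continued dosing would mean.** Section 6.6 states: "The dose increases between cohorts will be up to 100%, i.e. doubling of the dose". With a step of at most 100%, one reduction leaves at least 1 / (1 + 1.00) = 0.50 of the triggering dose. Two leave at least 1 / (1 + 1.00)² = 0.25. This assumes a once-daily schedule, that lower levels exist, and that the levels were reached under the doubling rule; 6.6 gives no figure for steps after the first qualifying toxicity.

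7. **Effect on dose finding.** Sections 6.5 and 6.8 count patients with DLTs. Once the event is scored as a DLT, it counts whether the patient is then reduced or stopped. Stopping for toxicity does not make the patient non-evaluable either, because 5.5 and 6.6 drop only patients under-dosed for reasons other than toxicity.

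**The case against.** The strongest reply is that Table 16 is part of the same binding protocol and is the specific rule, while 6.9.1 is the general one. Read together, the specific rule takes the patient off before any reduction arises, just as an excluded patient never reaches the 6.9.2 delay rule. Section 6.12 also offers a route: its ineligibility item can be read to cover a patient who meets an exclusion rule during treatment. In addition, the sites and the trials unit usually confer fortnightly (6.7.1), the Safety Review Committee reviews safety in both parts (6.7.2), and toxicities are reviewed and graded in real time (11.3.6).

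Much of this stands. It shows that the protocol can be read coherently and that an inconsistency might be caught. It does not make withdrawal operative in section 6. There, 6.9.1 is worded as a direction with no exception, 6.12 is permissive, and the only QTc eligibility criterion in 4.3 applies at baseline. A site following 6.9.1 literally would depart from Table 16.

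The objection is also right to resist three stronger readings:

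- A reader might infer that every QTc above 500 ms meets contradictory instructions. The documents support this only for an event scored as a DLT above 20 mg.
- A reader might take the 50% and 25% dose fractions, or the approximately 69 planned patients, as the size of the problem. The fractions restate the doubling rule and measure no risk. The 69 is the reach of Table 16, not of the conflict.
- A reader might infer that a single site ECG was meant to trigger permanent withdrawal. Table 16 does not say so, and the same cell specifies central analysis.

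**Conclusion.** The point holds in a limited form and should be corrected. Table 16 commits to an on-treatment stop that the available text of 6.9.1, 6.9.2, 6.12 and the ECG paragraphs does not carry. For a QTc above 500 ms scored as a DLT at a dose above 20 mg, section 6 directs reduction and implies continued dosing, with discontinuation left to discretion.

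The effect is on the safety of individual patients. A reader might suppose that the MTD or the escalation rule is compromised; the documents do not support that, since the DLT counts under either action. How many patients would be affected is unknown.

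The conclusion rests on two conditions: the event is scored as a DLT (through the assumed CTCAE grade or the Investigator's judgement), and the unseen flow charts do not themselves contain the stop. Confidence is medium.

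**What to change.** Add to 6.9.1: *Exception: a patient whose on-treatment QTcF becomes > 500 ms stops CCT3833 (Table 16); dose reduction does not apply.* List the same event in 6.12 as a mandatory discontinuation criterion, apart from the discretionary list. Cross-refer to it from 6.9.2 and from the ECG paragraphs of 8.1.2.2 and 8.2.2.1.

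In the same edit, settle two things that Table 16 leaves open:

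- Exclusion means stopping CCT3833, with off-study safety follow-up.
- Drug is held on the site Fridericia reading and discontinued permanently once the central ECG analysis named in Table 16 confirms a value above 500 ms. One sentence should say what follows if it is not confirmed.

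If the sponsor in fact prefers dose reduction for this event, Table 16 should be changed instead, so that the protocol gives one instruction.

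The cost is a few sentences and cross-references. No new patient assessment is needed, since Fridericia QTc is already reviewed. The ECG paragraphs do not describe the central reading, so its route to the site would need stating. The clinical downside is that a patient who might have tolerated a lower dose comes off drug, as Table 16 already provides.

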11.3.7 Regulatory compliance

The Sponsor and Chief/Principal Investigator must ensure that the trial is carried out in accordance with all the laws and statutes, as amended from time to time, applicable to the performance of Clinical Trials, including but not limited to the principles of ICH Harmonised Tripartite Guideline for GCP (CPMP/ICH/135/95) as set out in schedule 1 (Conditions and Principles of GCP for the protection of clinical trial subjects) of the Medicines for Human Use (Clinical Trials) Regulations 2004 (S.I 1031) and the GCP Directive 2005/28/EC as set out in the amended regulations 2006 (S.I 1928).

